9.5 Analysis of secondary variables

9.5.1 Efficacy variables

The primary analysis and the analyses of all secondary variables will be based on the ITT population.

PASI

Summary statistics for PASI 50, PASI 75, PASI 90, PASI 100 response by visit will be presented with absolute and relative frequencies.

The following definitions of PASI response will be used:

- PASI 50 response: subjects achieving \geq 50% improvement (reduction) in PASI score compared to baseline are defined as PASI 50 responders.
- PASI 75 response: subjects achieving \geq 75% improvement (reduction) in PASI score compared to baseline are defined as PASI 75 responders.

- PASI 90 response: subjects achieving $\geq 90\%$ improvement (reduction) in PASI score compared to baseline are defined as PASI 90 responders.
- PASI 100 response / remission: complete clearing of psoriasis (PASI=0).

Confidence intervals for response rates will be derived as well, based on the score method including continuity correction ([Newcombe 1998](#)).

Summary statistics will be provided for absolute PASI scores and for percent changes from baseline by visit and cohort. A graphical representation will also be provided.

The proportion of patients who reach PASI 75 after 16 weeks will be compared between cohorts with the same method presented for the primary endpoint.

The differences between cohorts in time to reach PASI 90, as well as PASI 75, will be evaluated by means of a log-rank test. The hazard ratios and their corresponding 95% confidence intervals will be also computed using a stratified Cox proportional hazards regression model with Cw6 group and baseline PASI as explanatory variable and stratified by geographical region and BMI, as well as the clinically relevant baseline variables. The Kaplan-Meier estimates of the cumulative rate for each cohort will be plotted.

IGA mod 2011

Summary statistics for the IGA mod 2011 score over time, as well as percent changes from baseline, will be presented by visit and cohort. Summary statistics for IGA 0 or 1 response by visit and cohort will be presented with absolute and relative frequencies. Subjects achieving IGA score 0 or 1 are defined as IGA 0 or 1 responders.

9.5.2 Safety variables

Vital signs

Summary statistics of vital signs and changes from baseline will be provided by visit and cohort. Clinically notable vital signs will be listed and absolute and relative frequencies will be presented by visit and cohort.

Height, weight and waist

Summary statistics will be provided for height, weight, waist and derived BMI (calculated from body weight and height) by visit and cohort including changes from baseline.

Hematology, clinical chemistry, urinalysis, hsCRP

Summary statistics of raw data and absolute and changes from baseline will be provided for laboratory data by visit and cohort.

Patients with values above (H) or below (L) notable criteria (see [Appendix 1](#)) will be listed and absolute and relative frequencies will be presented by visit and cohort. Laboratory values will be presented for each subject in a data listing with an indication of whether the value is above (H) or below (L) the normal reference range.

Laboratory data will also be summarized by presenting shift tables for each laboratory parameter showing the number and percentage of subjects in each cohort with the most extreme post-baseline value that falls outside normal ranges by the classification of value at baseline (H/N/L).

Adverse Events

A summary table of AEs will be produced by cohort specifying the number of total events and the absolute and relative frequency of patients with AEs. The absolute and relative frequency of patients with study drug related AEs, severe AEs, SAEs, AEs with an outcome of death, AEs leading to discontinuation of treatment will be also reported.

AEs will be tabulated also by System Organ Class, Preferred Term.

SAEs will be summarized as well.

All study drug related AEs, AEs with an outcome of death, AEs leading to discontinuation of treatment will be listed.

The above reported analysis will focus on treatment emergent adverse events. A treatment-emergent adverse event is defined as any adverse event that develops after initiation of the study treatments or any event already present that worsens following exposure to the study treatment. Non-treatment emergent adverse events will be listed separately.

9.5.3 Resource utilization

Data relating to health resources use will be used for the purpose of economic evaluation, particularly, to compare the amount of health resources used in the 6 months prior to the beginning of the study and during the study. Health resources use will refer to all items of assistance provided to the patients in the 6 months prior to the beginning of the study and during the study.

The analysis of health resources use will be conducted considering the patients' demographic characteristics, anthropometric parameters (such as weight, BMI and waist circumference), co-morbidities (such as anxiety and depression), and scores provided by the Study (such as PASI, DLQI, HADS).

The cost for all items of assistance provided to the patient and included into the economic evaluation will be calculated according to price (such as for drugs) or tariffs (such as for tests).

Given the skewed distribution of costs, median value will also be presented (in addition to mean value).

9.5.4 Health-related Quality of Life

Dermatology Life Quality Index

Seven scores will be derived from the DLQI: the total score of each of the six dimensions as well as the total score over all items. The higher the score, the more quality of life is impaired.

The percentage change from baseline will be derived for each of the seven scores. Summary statistics will be provided for absolute values as well as for the percentage change by visit.

Change from baseline will be analyzed by means of a pairwise test for categorical data.

In addition, summary statistics will be provided for the number of subjects achieving DLQI 0 or 1 at each time point.

Hospital Anxiety and Depression Scale

Descriptive statistics of HAD-A and HAD-D score at each time point with changes vs baseline will be provided.

The sub-scores, HAD-A and HAD-D, will be displayed per class (i.e. scores ≥ 11 indicate the presence of anxious or depressive disorders; scores between 8-10 points are borderline abnormal, and scores of ≤ 7 indicate that the disorder is not present) at each time point by means of a shift table.

In addition, the prevalence of anxiety and depression will be presented on the basis of the following three criteria: as per the score on the corresponding sub-scores of the HAD questionnaire, in terms of the treatment they are receiving for anxiety/depression, and according to both criteria.

[figure not shown]
A correlation between HADS and PASI will be explored by means of a Spearman coefficient (or Pearson, according to the data distribution). A cross-table for PASI90 or PASI75 and HAD score ≥ 11 at baseline and at 16 weeks will also be provided.

9.5.5 Pharmacokinetics

Not applicable.

9.5.6 Pharmacogenetics/pharmacogenomics

Not applicable.

9.5.8 PK/PD

Not applicable.

9.6 Interim analyses

Not applicable.

9.7 Sample size calculation

The primary objective of this study is to evaluate the clinical response in PASI 90 at week 16 of Cw6-negative and Cw6-positive psoriatic patients.

According to literature data, Cw6-positive patients will be about 60% of the entire psoriatic patient population.

From a previous study with ustekinumab (Talamonti et al. 2013) we can observe a difference in response to PASI 90 between Cw6-positive vs Cw6-negative patients of around 30%, in favor of Cw6-POS. Therefore, it is sensible to expect a response in the Cw6-negative cohort not less than 12 % respect to the Cw6-positive group. Further considerations are stated in the paragraph below.

Phase III data on secukinumab show a PASI 90 response at 16 weeks of 71%. Under the assumption that 60% of all the enrolled patient population is represented by Cw6-POS patients, we can reasonably assume to observe a proportion of patients with PASI 90 of 80% in the Cw6-POS cohort.

Under these assumptions, considering a one-side alpha level of 0.025 and a power of 80%, 365 patients (219 Cw6-POS and 146 Cw6-NEG) are sufficient to evaluate if the response in terms of PASI 90 in the Cw6-negative cohort is not less than 12% respect to the Cw6-positive cohort.

Considering a dropout rate at 16 weeks of 10% equally divided in the two studied cohorts, a total of 406 patients should be enrolled.

All calculations were done with NQuery 7.0.

A power analysis based on a different Cw6 patient distribution was made in order to facilitate patient enrollment without power-loss in the primary endpoint evaluation. Table 9-1 shows how the enrollment rate should be set free until the ratio between Cw6-POS and Cw6-NEG reaches the 1:1 rate-distribution, with a power of at least 80%.

In particular, the number of Cw6-POS evaluable patients will range from 219 to 182, whereas those in the Cw6-NEG cohort will range from 146 to 182.

Based on the table below, the enrollment in one of the two cohorts will be stopped when the target number is achieved (a maximum of 244 Cw6-POS patients will be allowed).

Table 9-1: Power analysis

Power	Ratio	Cw6 POS %	Cw6 NEG %	Cw6 POS N	Cw6 NEG N	Overall N	Drop out 10%	
							Cw6 POS N	Cw6 NEG N
80%	0,66	60%	40%	219	146	365	244	163
80%	0,70	59%	41%	215	150	365	239	167
80%	0,72	58%	42%	212	153	365	236	170
80%	0,75	57%	43%	209	156	365	233	174
81%	0,79	56%	44%	204	161	365	227	179
81%	0,82	55%	45%	200	165	365	223	184

81%	0,85	54%	46%	197	168	365	219	187
81%	0,89	53%	47%	193	172	365	215	192
81%	0,92	52%	48%	190	175	365	212	195
81%	0,96	51%	49%	186	179	365	207	199
81%	1,00	50%	50%	182	182	364	203	203

The choice of clinically relevant differences is based on the following considerations:

- As the efficacy of secukinumab has already been clinically substantiated through extensive Phase II and III programs, all patients will be treated with active drug using the same therapeutic regimen (no placebo comparison will be done).
- The primary variable is the proportion of patients who reach PASI 90 after 16 weeks. This endpoint is quite challenging and much more restrictive compared to PASI 75. Only the investigator is responsible for collecting the components or scoring signs and total regional areas in the PASI assessment. Therefore, it has great internal variability, which should be taken into account.
- The paper on HLA-Cw6 ustekinumab data ([Talamonti M et al. 20134](#)) revealed a striking difference between Cw6-positive and Cw6-negative patients in the proportion of PASI 90 achievements, 85.7% vs 56.5%. This difference in PASI 90 is very relevant in the daily clinical management of patients.

Considering the above statements, it seems reasonable to claim that more than halving the difference observed with ustekinumab between Cw6-positive and Cw6-negative patients, secukinumab would be an advantage in terms of efficacy for Cw6-negative patients who do not respond properly to ustekinumab and other approved biologic drugs.

Although the sample size was calculated considering only Cw6 haplotype, it is also adequate for regression models assessing differences from baseline for clinically relevant variables. In fact, the expected number of patients who reach PASI 90 at week sixteen is at least 250 (roughly 71% of 365). Therefore, using a conservative criterion of a minimum of 10 “events” for each predictor in the model, we can add up to 25 variables in the model without loss of power ([Vittinghoff E et al. 2007](#)). This model will take into account variables such as BMI, smoking, metabolic syndrome and TNF α -308 polymorphism, which, among the six existing polymorphisms, is the one most greatly affecting response to treatment with anti-TNF α drugs.

10 Ethical considerations

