	
Under these assumptions, considering a one-side alpha level of 0.025 and a power of 80%, 365 patients (219 Cw6-positive and 146 Cw6-negative) are sufficient to evaluate if the response in terms of PASI 90 in the Cw6 negative cohort is not less than 12% respect to the Cw6 positive cohort.
 
Considering a dropout rate at 16 weeks of 10% equally divided in the two studied cohorts, a total of 406 patients should be enrolled.
 
Although the sample size was calculated considering only Cw6 haplotype, it will also be adequate for a regression model assessing differences from baseline of clinically relevant variables such as BMI, metabolic syndrome, smoking and TNFα-308 polymorphism, which, among the six existing polymorphisms, is the one most greatly affecting response to treatment with anti-TNFα drugs.

Key words	Chronic plaque psoriasis, PASI, HLA determination, IL-17A, Cw6, secukinumab.

Amendment 3

The purpose of this amendment is to correct some minor inconsistencies found in the inclusion and exclusion criteria detailed in the study protocol. The paragraph 6.4.2 has also been corrected. The informed consent form has been updated in order to correct minor discrepancies with the study protocol.

Furthermore, we took advantage of this amendment in order to correct some typos present in the study protocol.

Amendment 2

The purpose of this amendment is to provide continued treatment of patients on secukinumab for an additional 48 weeks (overall up to 72 weeks), and thus allow for safety, tolerability, and efficacy data to be collected from the participating patients over a longer period of time. The extension period will allow meeting the following needs:

- 1) Investigate response sustainability to secukinumab after 72 weeks of continuous treatment.
- 2) Explore if HLA-CW6 can influence the kinetics of the response to secukinumab in the long term (ustekinumab data showed a faster response in CW6 positive patients compared with CW6 negative patients).

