A recently published paper demonstrated an association between the presence of the HLA-C*06 allele and the response to ustekinumab. The study showed an increased response to ustekinumab in Cw6-positive (Cw6POS) patients [PASI 75 at week 12: 96.4% in Cw6POS vs. 65.2% in Cw6-negative (Cw6NEG) patients; P = 0.008] and that HLA-Cw6POS patients

also responded faster to ustekinumab, 89.3% of them reaching PASI 50 at week 4, after a single injection (vs. 60.9% of HLA-Cw6NEG patients). The superior response of HLA-Cw6POS patients was maintained throughout the study period and reached the highest statistical significance for PASI 75 at week 28 (96.35% Cw6POS vs. 72.7% Cw6NEG; odds ratio 9.8). Analysis of TNFAIP3 rs610604 polymorphism and LCE3B/3C gene deletions did not show any significant association with response to ustekinumab (Talamonti M et al. 2013).

Secukinumab is a high-affinity human monoclonal anti-human IL-17A antibody of the IgG1/ κ isotype that demonstrated a favorable safety and tolerability profile with robust clinical activity in a series of Phase II studies, and is undergoing an extensive Phase III program (Gisoni P et al 2014). Secukinumab binds to human IL-17A and neutralizes its bioactivity by inhibiting IL17A produced by both Th17 cells and cells of the innate immune system, thus providing complete anti IL17A blockage. Targeting IL-17A has the potential to reduce autoimmune inflammation while leaving other immune functions undisturbed. While targeting of Th1-promoting or Th17-promoting cytokines affects critical mediators such as IFN- γ , IL-22 and IL-21, selective targeting of IL-17A leaves these Th1/17 activities, as well as certain protective functions of innate cells intact (Patel DD et al. 2013). Furthermore, as a fully human monoclonal antibody, secukinumab has low immunogenicity (i.e., antidrug antibodies) compared to current or emerging biologic therapies that are not fully human. Data linking secukinumab efficacy to a particular genetic biomarker are lacking. However, due to its mechanism of action, the efficacy of secukinumab should not be HLA restricted, and when considering the main haplotype associated with psoriasis, no difference between Cw6-negative and positive patients is expected.

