3.2 Rationale of study design

The efficacy of secukinumab, as well as the proposed dose/regimen, has already been clinically substantiated through extensive Phase II and III programs. Therefore, all patients will be treated with active drug using the same therapeutic regimen.

Recent research has revealed a marked difference in the proportion of PASI 90 achievers between Cw6-positive and Cw6-negative patients (85.7% vs 56.5%) treated with ustekinumab ([Talamonti M et al. 2013](#)) and a greater efficacy of anti-TNF α drugs in CW6 negative patients ([Galli E et al. 2013](#)). Unlike anti-IL-12/23 agents, secukinumab inhibits IL-17 produced by both Th17 cells after presentation by antigen presenting cells (in this case Cw6) and cells of the innate immune system whose activation does not require antigen presentation. If secukinumab were equally effective on both Cw6 negative and Cw6 positive patients, as its

mechanism of action suggests, this would be an important clinical accomplishment and would eliminate the need for costly HLA-Cw6 tests. The choice of a cohort study would therefore seem appropriate for this clinical context.

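### The 80% power in Protocol 9.7 and SAP 3 needs an unprinted 80% PASI 90 rate in both cohorts, which the section's own 71% overall rate contradicts; at 71% in both, power is about 70% to 71%

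*Protocol*

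**What the plan says.** Protocol 9.7, repeated in SAP 3, builds the sample size as follows. "Phase III data on secukinumab show a PASI 90 response at 16 weeks of 71" percent. Cw6-positive patients are taken to be 60% of those enrolled, and from this "we can reasonably assume to observe a proportion of patients with PASI 90 of 80% in the Cw6-POS cohort". On that basis, with one-sided alpha 0.025 and a 12-point margin, 219 Cw6-positive and 146 Cw6-negative evaluable patients are said to give 80% power. The synopsis carries the same conclusion: "365 patients (219 Cw6-positive and 146 Cw6-negative) are sufficient to evaluate" the question.

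Table 9-1 (SAP Table 3-1) gives 80% or 81% power for 11 splits, from 219/146 to 182/182. The text relies on it to let enrolment run freely until the ratio "reaches the 1:1 rate-distribution, with a power of at least 80" percent.

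Neither section prints a Cw6-negative rate or an assumed true difference. Other parts of the protocol address this in words only. Section 1.1 says that "no difference between Cw6-negative and positive patients is expected". Section 3.2 treats equal efficacy as what the mechanism suggests: "If secukinumab were equally effective on both Cw6 negative and Cw6 positive patients".

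The same sample-size section closes by justifying the regression model: "the expected number of patients who reach PASI 90 at week sixteen is at least 250 (roughly 71% of 365"), so that, at 10 events per predictor, "we can add up to 25 variables in the model without loss of power".

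**The concern.** Non-inferiority power for two proportions depends on both cohort rates. Only one is printed, so the stated power cannot be checked from the text as it stands. The rate that is printed is presented as following from 71% overall and a 60% share, but those two figures do not yield 80% in Cw6-positive without a further assumption about Cw6-negative. The section then uses 71% again as the expected rate for this trial's own 365 patients.

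The power statement and the freedom to drift to 1:1 are worded without conditions. If they hold only at a response level that the section does not support, anyone interpreting a failed non-inferiority result would overestimate how likely the trial was to succeed. The predictor allowance raises a separate question, because it counts the commoner of the two outcomes.

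**Working it through.** **Inputs.** One-sided alpha 0.025, Cw6-positive rate 80%, overall rate 71%, Cw6-positive share 60%, and the evaluable and enrolled numbers by row (Protocol 9.7, Table 9-1). Margin 0.12 (Protocol 9.4.2, SAP 2.5.2). Cw6-negative rate: not printed.

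**Formula.** The documents name nQuery 7.0 but no test. I used the unpooled normal approximation: power = Φ((0.12 − d)/SE − 1.96), with d = p_POS − p_NEG and SE = √[p_POS(1 − p_POS)/n_POS + p_NEG(1 − p_NEG)/n_NEG].

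**1. Reproduce the plan at 80%/80%.** At 219/146, SE = √(0.16/219 + 0.16/146) = 0.0427, and 0.12/0.0427 − 1.96 = 0.848, so power is 80.17%. The 11 rows give 80.17, 80.51, 80.73, 80.93, 81.21, 81.40, 81.51, 81.62, 81.68, 81.73 and 81.64. Truncated to whole percent, they match every printed value. Solving for n returns 219 and 146, and 365/0.9 gives 406.

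**2. Which Cw6-negative rate does the table need?** With Cw6-positive fixed at 80%, all 11 printed powers are matched only for Cw6-negative between 79.98% and 80.00% (truncation) or 79.91% and 79.94% (rounding). The dependence is steep: Cw6-negative at 79% gives 72% to 74% power, and at 71% it gives 9% to 10%. This step is conditional on the stated 80%. Other pairs, such as 74%/75%, also give about 80% at 219/146.

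**3. Compare with the section's own rates.**
- 80% in both cohorts is 80% overall: 292 responders of 365, against 0.71 × 365 = 259.
- Keeping 71% overall, the 60% share and 80% in Cw6-positive: p_NEG = (0.71 − 0.60 × 0.80)/0.40 = 57.5%. Then d = 22.5 points, beyond the margin. At 219/146, SE = 0.0490 and (0.12 − 0.225)/0.0490 − 1.96 ≈ −4.10, so power is about 0.002%.
- Keeping 71% overall and equal cohorts, as Protocol 1.1 expects, puts each cohort at 71%. At 219/146, SE = √(0.2059/219 + 0.2059/146) = 0.0485, and 0.12/0.0485 − 1.96 = 0.515, so power is 69.68%.

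| Rates (POS/NEG) | 365 evaluable, range over splits | All enrolled retained, range over splits |
|---|---|---|
| 80%/80% | 80.17% to 81.73% | 84.27% to 85.62% |
| 71%/71% | 69.68% to 71.42% | 74.35% to 75.97% |

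The right-hand column is an upper bound. It is relevant because the ITT analysis carries the last PASI forward for dropouts (Protocol 9.4.3, SAP 2.5.3).

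**4. Other methods at 71%/71%.** Exact enumeration with the Wald rule gives 69.6% at 219/146 and 71.6% at 182/182. Farrington-Manning, asymptotic or exact, gives about 68% to 72% on evaluable patients. A continuity correction gives 65% at 219/146.

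**5. Predictor allowance.** With a response rate above 50%, non-responders are the rarer outcome and limit a logistic model.
- At 71%: 0.29 × 365 ≈ 106, or 0.29 × 406 ≈ 118 if all are retained.
- At 80%: 0.20 × 365 = 73.
- At 10 per predictor this allows about 10 (11 if all are retained) or 7, against 25 stated.
- The PASI 90 model in SAP 2.5.2 has 12 variables including cohort. With two coefficients each for region, prior therapy and IGA and one for each of the other nine, that is 15 coefficients. At 71%, 106/12 = 8.8 non-responders per variable and 106/15 = 7.1 per coefficient.

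**The case against.** The arithmetic is sound: 365 is correct at 80%/80%. Planning a non-inferiority comparison at zero true difference is conventional, and Protocol 1.1 gives that expectation in words, so the missing Cw6-negative rate can be called a reporting gap. Nobody proposed 57.5% in Cw6-negative, and 71%/71% is not an assumption that the section states. The test behind nQuery is unnamed, and some formulas give less than 80% even at 80%/80%: 77.4% for asymptotic Farrington-Manning and 76.2% with a continuity correction, both at 219/146. The SAP was finalised late, and restating planned power changes no estimate or conclusion. The logistic model is supportive, has provisions for non-convergence and separation, and misses a rule of thumb only modestly.

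Much of this stands. The 57.5% figure shows only that the printed inputs cannot be combined; it is not a plausible power. The 71%/71% case is my combination of Protocol 1.1 with the 71% in 9.7. The 80%/80% reading is an inference, though one that fits every row, and the sponsor should confirm it.

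The conflict is not removed. The section presents 80% as a consequence of 71% and the share, and applies 71% to this trial's own 365. The wording that at least 250 responders are expected permits a floor, but 71% is still the rate offered as its basis. Zero difference alone does not give the printed power; a common rate of about 80% is also needed.

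**Conclusion.** The concern holds and should be fixed. The printed 80% to 81% power is correct only for an unprinted assumption of about 80% PASI 90 in both cohorts, which cannot stand beside the section's 71% overall rate. At 71% in both cohorts power is about 10 points lower: 69.7% to 71.4% on evaluable patients, and at most about 74% to 76% with all enrolled retained. These figures rest on the unpooled normal method, the stated 80% in Cw6-positive for the back-calculation, and equal cohorts at 71% for the comparison.

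The estimate, margin, decision rule and type I error are unaffected. The secondary point also holds: by the section's own rule the allowance is about 10 variables at 71%, or about 7 at 80%, not 25. Ten per predictor is a guide and not a hard limit.

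**What to change.** 1. In Protocol 9.7 and SAP 3, and in the synopsis wherever it repeats this text, state the assumptions behind the numbers: 80% PASI 90 in both cohorts and a true difference of zero, once confirmed against the nQuery record. Remove the derivation of 80% from 71% and the 60% share. Either justify 80% on separate grounds or label it optimistic relative to the Phase III rate.
2. Make the power claim, including the allowance to reach 1:1, conditional on 80%/80%. Add the power at 71%/71%: about 70% to 71% on evaluable patients, up to about 74% to 76% if all enrolled are retained. Table 9-1 and SAP Table 3-1 can keep their values, with a footnote naming the method and, if confirmed, saying that power is truncated to whole percent. Rows with a small Cw6-negative deficit would be a useful option.
3. Replace the 25-variable allowance with one counted on non-responders (about 10 at 71%, about 7 at 80%). Note that the SAP PASI 90 model, with 12 variables and about 15 coefficients, exceeds it.

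The cost is a few sentences and one footnote. No patients are added and the primary analysis does not change; the stated power becomes less favourable.
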